8.1.3.2. Planned Exploratory Efficacy Display Details*Hgb Variability*

The number and percentage of subjects with a Hgb value < 7.5 g/dL and the number of times a Hgb value < 7.5 g/dL occurs during the EP will be summarized by treatment group using central laboratory Hgb values and separately using HemoCue Hgb values. This summary will be presented using evaluable Hgb values only (see Section 10.6.3). The central laboratory summary will be considered the primary summary of this data.

The number and percentage of subjects with a >1 g/dL increase in Hgb over 2 weeks (assessed at Week 2, and Week 4) or a >2 g/dL increase in Hgb within any 4-week period from Week 4 to Week 52 will be summarized by visit and overall at Week 52 by treatment group using HemoCue Hgb values. This summary will be presented using evaluable Hgb values only (see Section 10.6.3).

The number and percentage of subjects with a >2 g/dL increase in Hgb within any 4-week period from Week 4 to Week 52 will be summarized by visit and overall at Week 52 by treatment group using central laboratory Hgb values. This summary will be presented using evaluable Hgb values only (see Section 10.6.3). The central laboratory summary will be considered the primary summary of this data.

The number and percentage of subjects with a >1 g/dL decrease in Hgb over 2 weeks (assessed at Week 2, and Week 4) or a >2 g/dL increase in Hgb within any 4-week period from Week 4 to Week 52 will be summarized by visit and overall at Week 52 by treatment group using HemoCue Hgb values. This summary will be presented using evaluable Hgb values only (see Section 10.6.3).

The number and percentage of subjects with a >2 g/dL decrease in Hgb within any 4-week period from Week 4 to Week 52 will be summarized by visit and overall at Week 52 by treatment group using central laboratory Hgb values. This summary will be presented using evaluable Hgb values only (see Section 10.6.3). The central laboratory summary will be considered the primary summary of this data.

The number and percentage of subjects with a Hgb value ≥ 12 g/dL and the number of times a Hgb value ≥ 12 g/dL occurs during the EP will be summarized by treatment group using central laboratory Hgb values and separately using HemoCue Hgb values. This summary will be presented using evaluable Hgb values only (see Section 10.6.3). The central laboratory summary will be considered the primary summary of this data.

The percentage of time Hgb is ≥ 12 g/dL and the percentage of time Hgb is ≥ 12 g/dL for subjects with at least one Hgb ≥ 12 g/dL during the EP will be calculated using the Rosendaal method as described in Section 8.1.2. The percentage of time Hgb is ≥ 12 g/dL during the EP will be summarized using mean, standard deviation, minimum, P25, median, P75, and maximum by treatment group. This summary will be presented using evaluable Hgb values only (see Section 10.6.3).

Iron Parameters

Hepcidin, ferritin, and total iron on-treatment values will be log-transformed (see Section 10.5.2) and summarized using geometric mean, coefficient of variation, minimum, P25, median, P75, and maximum for each scheduled visit by treatment group. Graphical summaries will be provided.

TSAT and TIBC on-treatment values will be summarized using mean, standard deviation, minimum, P25, median, P75, and maximum for each scheduled visit by treatment group. Graphical summaries will be provided.

Percent change from baseline in log-transformed (see Section 10.5.2) hepcidin, ferritin, and total iron on-treatment values will be summarized using geometric mean, 95% confidence interval, minimum, P25, median, P75, and maximum for each scheduled visit by treatment group. Graphical summaries will be provided.

Change from baseline in TSAT and TIBC on-treatment values will be summarized using mean, standard deviation, minimum, P25, median, P75, and maximum for each scheduled visit by treatment group. Graphical summaries will be provided.

Average quarterly IV iron dose/subject while on treatment will be summarized by presenting average monthly IV iron dose by quarter (see Section 10.6.3). Summaries will include mean, standard deviation, minimum, P25, median, P75, and maximum by treatment group. Graphical summaries will be provided.

Average quarterly TSAT while on treatment will be summarized by presenting average TSAT values for the quarters used to generate IV iron dose by quarter (see Section 10.6.3). Summaries will include mean, standard deviation, minimum, P25, median, P75, and maximum by treatment group. Graphical summaries will be provided.

Average quarterly ferritin while on treatment will be summarized by presenting average ferritin values by quarter (see Section 10.6.3). Summaries will include geometric mean, coefficient of variation, minimum, P25, median, P75, and maximum by treatment group. Graphical summaries will be provided.

The number and percentage of subjects that met the iron management criteria during the study while on treatment will be summarized by treatment group for each 3-month period of the study and across the entire study. There are two types of iron management thresholds: the first type requires that iron therapy be administered if subjects have ferritin and/or TSAT values that are too low; the second type requires that all iron (excluding multivitamins) must be stopped if ferritin and/or TSAT values are too high. It is also possible for a subject to meet starting and stopping criteria on the same day with a low ferritin and a high TSAT. These subjects will also be summarized (see Section 10.6.3). Assessment of meeting iron management thresholds will be made based on central laboratory data values at the scheduled visits for ferritin and TSAT assessments, according to the schedule outlined in the Time and Events table (see Section 10.2.1). Further, the subjects who met the threshold requiring iron administration to start or stop will while on IV iron be grouped by the action taken with iron therapy in the 8 weeks following the date the threshold was met (i.e., starting or increasing iron therapy, maintaining existing iron therapy, receiving no iron therapy, stopping or decreasing iron therapy with no increase see Section 10.6.3) according to concomitant medication records for IV iron.

RBC and Whole Blood Transfusions

Summary and analysis tables will use the ITT population.

The total number of on-treatment RBC and whole blood transfusion events, transfusions and units for each subject will be derived as described in Section 10.6.3.4.

The number of on-treatment RBC and whole blood transfusion events per subject, the number of subjects with at least one RBC and whole blood transfusion event, and total number of RBC and whole blood transfusion events will be summarized.

The number of on-treatment RBC and whole blood transfusions events per 100 patient years will be summarized by treatment group.

The number of on-treatment RBC and whole blood transfusions per 100 patient years will be summarized by treatment group.

The number of on-treatment RBC and whole blood units per 100 patient years will be summarized by treatment group.

The reason for transfusion events will be summarised.

The above summaries will be produced for the Evaluation Period and Week 52.

An analysis of time to first RBC or whole blood transfusion will be performed as described in Section 10.6.3.4., including a Kaplan-Meier plot.

Dose Adjustment Scheme

See Section 10.6.3 for additional details of dose adjustment scheme endpoints.

The assigned dose by visit will be summarized using mean, standard deviation, minimum, P25, median, P75, and maximum by treatment group.

The assigned dose by visit will also be summarized by treatment group using the number and percentage of subjects assigned to each dose level. Stacked bar graphs displaying assigned dose at all scheduled visits starting with Day 1 will be provided by treatment group.

The median assigned dose by treatment and visit will be displayed graphically for each scheduled study visit using a line plot. The line plot of median assigned dose along with the first and the third quartiles by time will include vertical reference lines to identify the EP as well as the number of subjects by treatment group contributing to each median value.

The following summaries of dose adjustments will be produced twice – the first time counting all dose adjustments, including adjustments related to periods of dose holds (i.e., IRT assignment of a 0-dose), the second time excluding dose adjustments related to periods of dose hold.

The number and percentage of subjects with 0, 1, 2, ..., 10, or >10 dose adjustments will be summarized by treatment group. Summaries will be presented for the following categories of time: Day 1 – < Week 28, Week 28 – <Week 52, and Day 1 – < Week 52.

The number of dose adjustments per subject will be summarized using mean, standard deviation, minimum, P25, median, P75, and maximum by treatment group. Summaries will be presented for the following categories of time: Day 1 – < Week 28, Week 28 – <Week 52, and Day 1 – < Week 52.

The time (in days) that study treatment was withheld for Hgb values ≥ 12 g/dL per subject will be summarized for all subjects and for subjects who had a dose hold using mean, standard deviation, minimum, P25, median, P75, and maximum by treatment group. Summaries will be presented for the following categories of time: Day 1 – < Week 28, Week 28 – <Week 52, and Day 1 – < Week 52.

Summary tables for the dose adjustment scheme endpoints will also be repeated for the following subgroups (see Section 10.10.1 for subgroup definitions):

- Dialysis type at randomization
- Dialysis start manner
- Baseline weight quartiles

The median most recent dose by treatment and visit will be displayed graphically for each scheduled study visit using a line plot. The line plot of median most recent dose along

CONFIDENTIAL

201410

with the first and the third quartiles by time will include vertical reference lines to identify the EP as well as the number of subjects by treatment group contributing to each median value. This plot will be overlaid on a graph of corresponding mean Hgb values by visit

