
 To compare daprodustat to rhEPO on the symptom severity and change 	
 Change from Baseline at Wk 52 by domain and overall symptom score on the CKD-AQ Change from Baseline at Wk 8,12, 28, 52 in PGI-S

 To summarize the PK parameters of daprodustat and three major metabolites in dialysis subjects 	
 Plasma daprodustat, M2, M3, and M13 PK parameters pre-dose trough (Ctau) and Cmax
Exploratory Objectives	Exploratory Endpoints (Statistical testing not planned)

 To further compare daprodustat and rhEPO on Hgb variability 	
 Hgb observed and change from baseline across all visits to end of treatment % of time Hgb is above, within and below the analysis range (10-11.5 g/dL) during EP Number (%) of subjects with mean Hgb above, within and below the Hgb analysis range during EP and at the end of treatment Number (%) of subjects with a Hgb <7.5 g/dL during the EP Number of times Hgb <7.5 g/dL during the EP Number (%) of subjects with a >1 g/dL increase in Hgb over 2 weeks (assessed at Week 2 and Week 4) or a >2 g/dL increase in Hgb within any 4-week period from Week 4 to Week 52 Number (%) of subjects with a >1 g/dL decrease in Hgb over 2 weeks (assessed at Week 2 and Week 4) or a >2 g/dL decrease in Hgb within any 4-week period from Week 4 to Week 52 N (%) of subjects with a Hgb value \geq 12 g/dL during the EP Number of times Hgb \geq 12 g/dL during the EP % of time Hgb \geq12 g/dL during the EP

CONFIDENTIAL

201410

Objectives	Endpoints

 To compare daprodustat to rhEPO on measures of iron parameters 	
 Observed and change from baseline in hepcidin, ferritin, transferrin saturation, total iron, total iron binding capacity (TIBC) across all visits to end of treatment Average quarterly TSAT Average quarterly ferritin Average quarterly IV iron dose/subject N (%) of subject who met iron management criteria

 To compare daprodustat to rhEPO on the need for RBC and whole blood transfusions 	
 Number (%) of subjects who receive at least one RBC or whole blood transfusion by Week 52 Number of RBC and whole blood transfusions per 100 patient years Number of RBC and whole blood units per 100 patient years

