8.1.3. Exploratory Efficacy Analyses

8.1.3.1. Overview of Planned Exploratory Efficacy Analyses

Table 7 provides an overview of the planned exploratory efficacy analyses.

Table 7 Overview of Planned Exploratory Efficacy Analyses

Endpoint	Analysis Population	Absolute				Change from Baseline			
		Summary		Individual		Summary		Individual	
		T	F	F	L	T	F	F	L
Hgb Variability									
Hgb observed (including imputed) and change from baseline (CFB) cross all visits to end of treatment	ITT	Included with Hgb primary and supportive analyses (Section 7.1)							
% of time Hgb is above, within and below Hgb analysis range (10-11.5 g/dL) during EP	ITT	Included with Hgb secondary analyses (Section 8.1.2)							
Number (%) of subjects with mean Hgb above, within and below Hgb analysis range during EP and at the end of treatment	ITT	Included with Hgb secondary analyses (Section 8.1.2)							

CONFIDENTIAL

201410

Endpoint	Analysis Population	Absolute				Change from Baseline			
		Summary		Individual		Summary		Individual	
		T	F	F	L	T	F	F	L
Number (%) of subjects with Hgb < 7.5 g/dL during EP ¹	ITT	Y							
Number of times Hgb < 7.5 g/dL during EP ¹	ITT	Y							
Number (%) of subjects with a >1g/dL increase in Hgb over 2 weeks (assessed at Week 2 and Week 4) or a >2 g/dL increase in Hgb within any 4 week period from Week 4 to Week 52 ¹	ITT	Y							
Number (%) of subjects with a >1g/dL decrease in Hgb over 2 weeks (assessed at Week 2, Week4, Week6, and Week 8) or a >2 g/dL decrease in Hgb within any 4 week period from Week 4 to Week 52 ¹	ITT	Y							
N(%) of subjects with a Hgb value ≥ 12 g/dL during the EP ¹	ITT	Y							
Number of times Hgb ≥ 12 g/dL during the EP ¹	ITT	Y							
% of time Hgb ≥ 12 g/dL during the EP ¹	ITT	Y							
Iron Parameters									
Hepcidin, ferritin, TSAT, total iron, TIBC observed and CFB cross all visits to end of treatment	ITT	Y	Y			Y	Y		
Average quarterly IV iron dose/subject	ITT	Y	Y						
Average quarterly TSAT	ITT	Y	Y						
Average quarterly ferritin	ITT	Y	Y						
Subjects who met iron management criteria	ITT	Y							
RBC and Whole Blood Transfusions									
Number (%) of subjects receiving at least one RBC or whole blood transfusion by Week 52	ITT	Y							
Number of RBC and whole blood transfusion events per 100 patient years	ITT	Y							
Number of RBC and whole blood transfusions per 100 patient years	ITT	Y							
Number of RBC and whole blood units per 100 patient years	ITT	Y							

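### SAP 8.1.3.2 defines the HemoCue table of large hemoglobin falls with a 4-week rise as its second component; separately, Table 7 gives different weeks for the 2-week fall

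*SAP*

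**What the plan says.** Five places in the current text describe the summary of large hemoglobin falls.

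- **SAP 2.2** lists the exploratory endpoint as a fall above 1 g/dL or above 2 g/dL, depending on the interval: "decrease in Hgb over 2 weeks (assessed at Week 2 and Week 4) or a >2 g/dL decrease in Hgb within any 4-week period". **Protocol Appendix 2** defines it the same way.
- **SAP 8.1.3.1, Table 7** keeps a fall in both components but lists more visits for the first: "decrease in Hgb over 2 weeks (assessed at Week 2, Week4, Week6, and Week 8". Its row for rises stays at Weeks 2 and 4.
- **SAP 8.1.3.2, HemoCue paragraph on falls** reads "decrease in Hgb over 2 weeks (assessed at Week 2, and Week 4) or a >2 g/dL increase in Hgb within any 4-week period".
- **SAP 8.1.3.2, central laboratory paragraph on falls** has the 4-week component only: "The number and percentage of subjects with a >2 g/dL decrease in Hgb within any 4-week period from Week 4 to Week 52". It adds: "The central laboratory summary will be considered the primary summary of this data".

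For comparison, the HemoCue paragraph on rises in 8.1.3.2 reads "increase in Hgb over 2 weeks (assessed at Week 2, and Week 4) or a >2 g/dL increase in Hgb within any 4-week period".

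**The concern.** Section 8.1.3.2 is where the SAP spells out the content of each display. Its HemoCue paragraph on falls joins a 2-week fall to a 4-week rise, which no statement of the endpoint does. A table built from it would carry the label of one endpoint and count another, and a 4-week rise would enter both the table of rises and the table of falls.

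HemoCue values are also the ones that drive dose adjustment (Protocol 6.2.3). This is therefore the display of falls on the same measurements that the dosing algorithm uses.

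The weeks in Table 7 raise a second, independent question: which visits count for the 2-week fall. The SAP's list of changes from the protocol (Table 1) mentions neither the direction nor the weeks.

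**Working it through.** No sample size, power or error rate is involved. The check sets the definitions side by side and then works out which subjects would be misclassified.

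**Step 1: compare the definitions.**

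| Source | Weeks for the 2-week fall | Direction of the 4-week component |
|---|---|---|
| Protocol Appendix 2 | 2, 4 | fall |
| SAP 2.2 | 2, 4 | fall |
| SAP Table 7 | 2, 4, 6, 8 | fall |
| SAP 8.1.3.2, HemoCue | 2, 4 | **rise** |
| SAP 8.1.3.2, central laboratory | none | fall |

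On direction, four of five sources agree and the HemoCue paragraph is the exception. On weeks, three of the four sources with a 2-week component agree and Table 7 is the exception. The protocol's record of amendment changes describes superseded text and is not counted.

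**Step 2: who would be misclassified.** For each subject, using HemoCue values, let

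- A = a 2-week fall above 1 g/dL at Week 2 or 4,
- B = a 4-week fall above 2 g/dL,
- C = a 4-week rise above 2 g/dL.

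The endpoint is (A or B). The HemoCue paragraph as written gives (A or C). There are 2 × 2 × 2 = 8 patterns.

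- With A present (4 patterns), both rules count the subject.
- With A absent and neither B nor C, neither rule counts the subject.
- With A absent and both B and C, both rules count the subject.
- With A absent, B absent and C present, the subject is **counted wrongly**.
- With A absent, B present and C absent, the subject is **missed**.

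So 2 of the 8 patterns are misclassified. In each arm the overall count is off by (number with C only) − (number with B only). The documents give no rates for these events, so neither the size nor the sign of that difference can be stated.

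**Step 3: the by-visit rows.** The table is to be presented by visit as well as overall. After Week 4 the HemoCue paragraph has no 2-week component left. If each row counts events at that visit, which the SAP does not spell out, every row after Week 4 would show rises only and repeat the corresponding row of the HemoCue table of rises.

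**Step 4: can the central laboratory table stand in?** Only in part. It shows the 4-week falls correctly but has no 2-week component. The Time and Events table explains why: at Weeks 2 and 6 HemoCue hemoglobin is scheduled and central hematology is not. The HemoCue table is therefore the only planned display of the composite endpoint.

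**The case against.** The strongest reply is that this is a copying slip of little weight. The faulty half repeats the second half of the HemoCue paragraph on rises, and a careful programmer would probably query it. The documents do not say which SAP section governs programming, and Table 7 has the right direction. The designated primary table captures the 4-week falls, and the endpoint sits among those for which no testing is planned. All of this stands and it limits the weight of the point. It does not make the paragraph correct, and it does not settle the weeks.

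The Table 7 weeks may even be deliberate. Footnote 4 of the dose-adjustment scheme (Protocol Appendix 3) applies its 2-week rule at Weeks 2, 4, 6 and 8. That is a reason to ask the sponsor which set is meant, not to assume an error. Against it, the Table 7 row for rises was not extended in the same way.

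Three stronger readings are tempting, and the documents do not support them.

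- *The tables of rises and falls would cover different visits.* Both HemoCue paragraphs in 8.1.3.2 use Weeks 2 and 4. The visits differ only if Table 7 is followed, and Table 7 has the right direction. A table programmed from one source would have one fault or the other, not both.
- *The differing weeks help make the HemoCue table miss its endpoint.* The weeks in 8.1.3.2 match SAP 2.2 and Protocol Appendix 2. Only the direction word makes that paragraph depart from the endpoint.
- *All large 4-week falls would go unreported.* The omission is confined to the HemoCue table, and even there a subject who also has a qualifying 2-week fall is still counted.

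**Conclusion.** The point holds as an internal inconsistency of minor weight. The HemoCue paragraph on falls in SAP 8.1.3.2 has the wrong direction in its 4-week component. Followed literally, it would give a table that matches no definition of the endpoint in either document. The Table 7 weeks are a separate discrepancy.

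The effect is limited to one untested exploratory display. Its 2-week component is in the right direction, and the primary, principal secondary and other tested results are untouched. The conclusion rests on two assumptions: that the table would be programmed from the text of 8.1.3.2, and that no table shell outside these documents already corrects it.

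**What to change.** 1. In the HemoCue paragraph on falls in SAP 8.1.3.2, change *increase* to *decrease* in the 4-week component.
2. Use one set of weeks for the 2-week fall in SAP 2.2, Table 7 and 8.1.3.2. Weeks 2 and 4 match the protocol endpoint, which means editing the one Table 7 entry. If Weeks 6 and 8 are intended, add them in 2.2 and 8.1.3.2, record the change with its reason in SAP Table 1, and say whether the endpoint for rises changes too.

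The cost is one word and, if Weeks 2 and 4 are kept, one table entry. No new data or analysis is needed. The edits are best made before the table is programmed and the study is unblinded.

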6.10. Iron Management Criteria

Subjects must remain iron replete throughout the study. The investigator will follow the iron management criteria from randomization (Day 1) through the end of the study treatment period for subjects receiving randomized treatment.

Iron therapy will be administered if ferritin is ≤ 100 ng/mL and/or TSAT is $\leq 20\%$. The investigator should choose the route of administration and dose of iron based on the subject's iron status and local clinical practice.

All iron (excluding multivitamins) must be stopped and cannot be administered if:

- Ferritin > 800 ng/mL and TSAT $> 20\%$, or
- TSAT $> 40\%$

Investigators should be guided by local/regional guidelines and may stop administration of iron at a lower ferritin or TSAT level as long as subjects are maintained at a ferritin > 100 ng/mL and TSAT $> 20\%$.

The Steering Committee (Section [10.8.3](#)) will monitor blinded subject iron data in an ongoing fashion to ensure compliance.

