10.6.3.2. Iron Endpoints

Iron Endpoints
Iron Medications

 During the study, subjects may be receiving iron in multiple routes, including: 
 IV iron Oral iron Other iron (including intramuscular, subcutaneous, and hemodialysis/dialysate) Note: The iron route categories above will be determined using the route on the Prior/Concomitant Medication – Iron Therapy record. In addition, ferric citrate records recorded on the Prior/Concomitant Medication – Metabolic Bone Disease Therapy eCRF form will also be summarized as oral iron use.
Baseline Iron Use

 The number and percentage of subjects in the following iron use categories at baseline will be summarized: 
 IV iron use only Oral iron use only Other iron use only IV and oral iron use only IV and other iron use only Oral and other iron use only

CONFIDENTIAL

201410

Iron Endpoints	

 ○ IV, oral, and other iron use ○ No iron use ● When determining baseline iron use, the gap factors mentioned below in the IV iron standardization algorithm will be applied to the end date for each iron record, and the baseline period of 10 weeks before the Randomization date until the day before the Randomization date will also be used. 	
Standardized IV Iron Dose (mg/week) to Determine Iron Management Action	

 ● In order to compare between IV iron records, to determine the action taken with IV iron therapy in the 8 weeks following the date the IV management threshold was met, the dose of IV iron in each associated record will be standardized in terms of mg/month. ● IV iron therapy concomitant medication records that occur or are ongoing during the 8 weeks following the date the IV management threshold was met (inclusive), will be selected and ordered by start and end date. 
 ○ If there is a record has a start date on the date the IV management threshold was met, and a prior record has an end date on the day before the IV management threshold was met, this prior record will be selected and considered as well. ● The standardization will be carried out with the following formula: 
 ○ Standardized IV iron dose (mg/week) = IV iron drug dose (mg) * frequency 	
Note: Frequency defined as follows:	
Frequency (from eCRF)	Frequency (for standardization formula)

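### The table of actions taken after an iron management threshold is built from IV iron records only, although the protocol's iron rules cover every route

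*SAP*

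**What the plan says.** Protocol 6.10 sets two rules for subjects on randomized treatment. Iron is to be given when ferritin is ≤100 ng/mL and/or TSAT is ≤20%, and on route it says: "The investigator should choose the route of administration and dose of iron". At the upper thresholds (ferritin >800 ng/mL with TSAT >20%, or TSAT >40%) it says: "All iron (excluding multivitamins) must be stopped and cannot be administered if" either condition is met. Neither rule is limited to IV iron.

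SAP 8.1.3.2, under Iron Parameters, restates the upper rule in the same terms: "the second type requires that all iron (excluding multivitamins) must be stopped". After counting subjects who meet a threshold, it says that they "will while on IV iron be grouped by the action taken with iron therapy" over the next 8 weeks. The categories are starting or increasing, maintaining, and then "receiving no iron therapy, stopping or decreasing iron therapy with no increase". The labels carry no route, but the data source does: "according to concomitant medication records for IV iron".

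SAP 10.6.3.2 shows that this is not a slip of wording. Its derivation exists "to determine the action taken with IV iron therapy in the 8 weeks following the date the IV management threshold was met", and the records it takes are "IV iron therapy concomitant medication records that occur or are ongoing during the 8 weeks following the date the IV management threshold was met". The same section recognises IV, oral and other routes, determines the route from the medication record, and counts ferric citrate as oral iron.

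**The concern.** The table is the planned display that ties a low or high iron result in a subject to what was done about it. Its labels speak of iron therapy, and the rules behind it concern iron by any route, but the classification sees only one route. A reader of the study report would take the categories at face value. Some responses that fit protocol 6.10 would look like inaction or withdrawal of iron, and some continued iron after a stop threshold would look like a stop. The trial is open-label and the investigator picks the route, so oral use could differ between arms. The table could then give an uneven picture of how the iron rules were followed.

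**Working it through.** No arithmetic applies, because the plan gives no figure on this point. The check is to take each plausible response to a threshold, set it against protocol 6.10, and apply the IV-only selection in SAP 10.6.3.2.

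| Threshold met | What happens in the next 8 weeks | Under protocol 6.10 | What the SAP table shows |
|---|---|---|---|
| Low | IV iron replaced by oral iron | Iron is being given | Stopping or decreasing |
| Low | Oral iron added to unchanged IV iron | Iron is being given, and more of it | Maintaining |
| Low | Oral iron started, no IV record | Iron is being given | No iron, or omitted |
| Stop | IV iron stopped, oral iron continues | Not all iron has stopped | Stopping or decreasing |
| Stop | Oral iron only, continues | Not all iron has stopped | No iron, or omitted |

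The two entries marked as omitted turn on the phrase "will while on IV iron be grouped by the action taken with iron therapy". The sentence is garbled. One reading confines the grouping to subjects on IV iron when the threshold is met, so oral-only subjects leave the denominator. The other treats the phrase as misplaced. An oral-only subject then has no selected record, and only the no-iron category fits. The second reading agrees better with the list of categories, since both starting and receiving none describe subjects who are not on IV iron. The text does not settle it.

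The other three rows do not depend on this. Those subjects are on IV iron when the threshold is met, so they are in the table under either reading and are classified by IV records alone.

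Next, whether another display fills the gap. SAP 10.6.3.2 defines iron use by route and quarter (IV only, oral only, other only, combinations, none). SAP 8.1.3.2 plans quarterly TSAT and ferritin by arm, and SAP 6.2.5 tabulates on-treatment medications by class and ingredient. These can show a group-level shift towards oral iron. None starts from the date on which a subject met a threshold, so none links that event to a non-IV response.

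Finally, where the table feeds. The principal secondary ANCOVA (SAP 8.1.1.2) uses IV iron dose per month, not the action categories. The per-protocol exclusion for iron status (SAP 10.1.1) uses ferritin and TSAT values. SAP 2.2 lists the iron management endpoint as exploratory, with no test planned. No confirmatory analysis takes this table as input.

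**The case against.** The strongest reply is that the IV scope is deliberate. The SAP 10.6.3.2 heading names IV iron dose, the text speaks of action with IV iron, and SAP 8.1.3.2 never calls the table a compliance check. On that view the fault is a missing label. This stands in part: a label would stop the table from misleading. It would not let the table answer the rule that the same paragraph restates, which covers all iron.

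The reply also says that oral-only subjects may be left out rather than misclassified. That is fair, and the point is worded to allow for it.

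Third, the plan is not blind to oral iron. The route-by-quarter summary covers much of the group-level question, and the Steering Committee monitors blinded iron data during the study. What remains uncovered is the link from an individual threshold to a non-IV response.

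Fourth, classifying an increase by any route would need dose rules for oral iron that the SAP does not have. Dose standardisation is defined for IV iron only. This objection stands, and the fix is narrowed accordingly.

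A reader might go further and infer that the IV iron superiority result depends on this table, or that the plan cannot distinguish less need for iron from iron given by mouth. The documents do not support either. The ANCOVA does not use the table, and the quarterly summaries address the second question at group level.

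**Conclusion.** The point holds as a low-priority correction. Followed as written, the SAP mislabels switches from IV to oral iron after a low threshold, and IV stops with oral iron continuing after a stop threshold. It also either mislabels or omits subjects whose only iron is oral. The affected share is the share of threshold events with a non-IV response. The documents give no figure for oral use, so any percentage would be a guess and none is offered. The conclusion assumes that some subjects receive oral or other iron during treatment, which SAP 10.6.3.2 itself allows for. The primary and principal secondary results and the per-protocol population are unaffected. What suffers is a descriptive table and a reader's view of how the iron rules were applied in each arm.

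**What to change.** Amend SAP 8.1.3.2 and 10.6.3.2 as follows.

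- State the denominator: all subjects who meet a threshold while on treatment. Remove or rewrite the phrase about being on IV iron.
- For low thresholds, classify each event as any iron started or continuing versus none, from all iron records (IV, oral including ferric citrate, and other; multivitamins excluded), with the route shown.
- For stop thresholds, count all iron as stopped only if no route continues. Say when within the 8 weeks a record must end to qualify.
- Keep the increase and decrease grouping for IV iron only, in a separate panel labelled as IV iron action.
- While editing, define the action categories, which SAP 8.1.3.2 refers to Section 10.6.3 but which are not defined there. Also settle the unit of the standardised dose for this derivation, which SAP 10.6.3.2 gives as both mg/week and mg/month.

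The cost is a little extra definition and programming. No new data are needed, because the route is already recorded and categorised, and no clinical rule changes. If even that is unwanted, the minimum is to state the denominator and title the table as IV iron action. That removes the misleading labels but leaves non-IV responses unseen.
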